6. GENERAL ANALYSIS DEFINITIONS

6.1 TREATMENT(S)

Daily single oral doses of afatinib will be investigated in this study for paediatric patients. Dose escalation starts at 80% of the adult MTD by m^2 BSA and allometric scaling (Level 0) and can be escalated to 100% (level 1), 125% (level 2) and 150% (level 3) of the adult dose if required. In case level 0 exceeds the MTD, a dose level -1 will allow de-escalation to 50% of the adult MTD dose by m^2 BSA and allometric scaling. Oral solution is available for younger children and patients who cannot swallow afatinib film coated tablets.

Analysing treatment periods are defined in Table 6.1: 1 for reporting of treatment emergent AEs and safety laboratory data. An adverse event will be assigned to the analysing period where start date \leq onset date of AE < stop date.

Table 6.1: 1 Definition of analysing treatment periods

Analysing treatment period	Start date (including)	Stop date (excluding)
Screening	Date of informed consent	Date of first intake of study drug
Course 1	Date of first intake of study drug	Start date of Course 2, or date of first intake of study drug + 28 days if the patient did not start Course 2
On-treatment	Date of first intake of study drug	Date of last intake of study drug + 29 days
Residual effect period (REP)	Date of last intake of study drug + 1 day	Date of last intake of study drug + 29 day
Off-treatment	Date of last intake of study drug + 29 day	Date of last follow up visit + 1 day or date of death + 1 day whichever occurred first

The residual effect period (REP) for afatinib is 28 days after last intake of afatinib. Data recorded between the first study drug intake until up to 28 days after the last study drug intake will be considered as on-treatment.

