Informed consent /patient assent	x ⁵											
Demographics	x											
Medical history	x											
Physical examination including neurological exam in patients with brain tumours	x	x	x	x	x	x	x	x	x	x		
Ophthalmologic examination	x									x		
Pulmonary examination ⁶	x	x					x		x	x		
Performance score ²²	x	x					x		x	x		
Vital signs	x	x	x	x	x	x	x	x	x	x		
Height ⁷	x								x ⁷			
Weight	x	x		x	x	x	x	x	x			
Safety laboratory tests ⁸⁻⁹	x	x ⁸		x ⁹	x ⁹	x ⁹	x	x ⁹	x	x ⁸		
Pregnancy test (if appl.) ¹⁰	x									x		
12 lead-ECG ¹¹	x			x					x ¹¹	x		
LVEF echo	x						x		x ¹²	x		
Disease assessment imaging ¹³	x								x ¹³	x		
Tumour marker(s) ¹⁴	x						x		x	x		
Tumour sample tissue availability ²³	x											
Review in-/ex- criteria	x											
Dose assessment	x						x ¹⁵	x ¹⁵	x ¹⁵			
Dispense trial drug ¹⁶		x					x		x			
Afatinib administration		Continuous oral once daily, fasted										
Pharmacokinetics		x ¹⁷	x ¹⁷	x ¹⁷	x ¹⁷							
Adverse events	x	x		x	x	x	x ¹⁸	x	x	x	x	x ¹⁹
Concomitant therapies	x	x		x	x	x	x	x	x	x	x	
Compliance check				x			x		x	x		
Patient diary check			x	x	x	x	x		x	x		
Eligibility for treatment continuation							x		x			
Conclusion of treatment										x		
Conclusion of patient participation											x	
Survival status												x

- All courses are of 4 weeks duration (28 days). Day 1 of a new course should take place on day 29. Patients may continue on treatment for unlimited courses until the criteria for stopping medication are met (see [Section 3.3.4](#)). Visits are performed weekly for the first course. At course 2, visits will take place every 2 weeks ([Visit 2 day 8](#) and visit 4 day 22 are no longer requested). From course 3 onwards, only visits “1” are required.
- EOT= end of treatment – When the decision is taken to permanently discontinue the study medication, the EOT visit must be performed within 7 days after last administration of afatinib. If the decision is taken at a scheduled visit, the EOT visit will be performed instead of the scheduled visit. Examinations performed at this time may need to be renamed for the actual visit conducted.
- FU= safety follow-up 28 to 30days after last afatinib administration. With the FU visit the patient will have completed his/her trial participation.
- OP= observation (post-trial) period. Collection of information on vital status every 3 months. Information could be collected from the patient’s notes or by telephone contact. A formal visit is not required.

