5.2.2.2 Adverse event and serious adverse event reporting

The residual effect period (REP) for afatinib is 28 days after last intake of afatinib.

All adverse events, serious and non-serious, occurring from signing of the informed consent/patient assent for trial participation onwards until the FU visit i.e. 28-30 days after last administration of study medication, regardless of relatedness and listedness, will be collected, documented and reported to the sponsor by the investigator.

SAEs and AESIs occurring after the FU visit (28-30 days after last administration of study medication) will be reported in case they are considered relevant by the investigator.

All AEs, including those persisting after end of study medication must be followed up until they have resolved or have been sufficiently characterised, unless the sponsor and the investigator agree not to pursue them further. Reporting will be done according to the specific definitions and instructions detailed in the adverse event reporting section of the ISF. A summary of the AE reporting requirements is given in [Table 5.2.2.2:1](#).

Proprietary confidential information.

© 2017 Boehringer Ingelheim International GmbH or one or more of its affiliated companies. All rights reserved.

This document may not - in full or in part - be passed on, reproduced, published or otherwise used without prior written permission.

Table 5.2.2.2:1 AE/SAE reporting requirements

Time period	Reporting requirements
From signing of informed consent for trial participation* to the FU visit (\leq 28-30 days after last trial drug administration) *Does not apply to pre-screening consent	Report all AEs and SAEs regardless of relatedness or whether the trial drug was administered. This includes all deaths.
Post-treatment: after the FU visit ($>$ 28-30 days after last trial drug administration)	Report only SAEs which are considered relevant by the investigator

The investigator must report the following events via fax using the SAE form immediately (within 24 hours) to the sponsor:

- SAEs
- non-serious AEs which are relevant for the reported SAE/AESI
- protocol-specified AESIs

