7.3.3 Safety analyses

DLTs will be tabulated for each dose cohort in the Phase I dose finding part. The tabulation will be done in two ways: (1) DLTs with onset in the first treatment course; (2) all DLTs regardless of treatment course at onset. The definition of DLT is defined in [Table 4.1.4.1:2](#).

Events that started within the course of treatment, starting after the first administration of the treatment and until 28 days after the last administration of treatment will be considered as having occurred on treatment. In general later events will be attributed to the post-study period and will be presented separately. However post-study events will be examined to determine whether they need to be combined with on-treatment events in an additional table.

Adverse events will be graded according to CTCAE v3.0 and reported according to BI standards. Serious adverse events will be tabulated. In addition, events leading to dose reduction or treatment discontinuation will be examined, but may not be reported as individual tables, depending upon the extent of overlap.

Descriptive statistics will be used to describe changes in laboratory parameters over time. In addition, all abnormalities of potential clinical significance will be reported. In general, potential clinical significance is defined as at least CTCAE Grade 2 and an increase in

Proprietary confidential information.

© 2017 Boehringer Ingelheim International GmbH or one or more of its affiliated companies. All rights reserved.

This document may not - in full or in part - be passed on, reproduced, published or otherwise used without prior written permission.

CTCAE classification from baseline. The incidence and intensity of adverse events will be correlated descriptively with pharmacokinetic data if possible.

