7.8.1 Adverse events

The analyses of adverse events (AE) will be descriptive in nature. All analyses of AEs will be based on the number of patients with AEs and not on the number of AEs. For analysis of duration, severity etc. of multiple AE occurrences, data on the case report form (CRF) will be collapsed into AE episodes provided that all of the following applies:

- The same MedDRA lowest level term was reported for the occurrences.
- The occurrences were time-overlapping or time-adjacent (time-adjacency of two occurrences is given if the second occurrence started on the same day or on the day after the end of the first occurrence).
- Treatment did not change between the onset of the occurrences or treatment changed between the onsets of the occurrences, but no deterioration was observed for the later occurrence.

For further details on summarization of AE data, please refer to the BI guideline (4).

The analyses of adverse events will be based on the concept of treatment-emergent adverse events. That means that all adverse events occurring between first drug intake and 28 days after last drug intake or death, whichever occurs first, will be assigned to the on-treatment period. All adverse events occurring before any study drug intake will be assigned to 'screening' and all adverse events occurring after last study drug intake + 28 days will be assigned to 'Off-treatment' (for listings only). For details on the treatment definition, see [Section 6.1](#).

An overall summary of adverse events will be presented. The frequency of patients with adverse events will be summarised by highest CTC grade (grades 1, 2, 3, 4, 5 and all grades), treatment, primary system organ class and preferred term for each of the following AE tables as well as relatedness of AEs to treatment and seriousness:

- DLTs (1st course and all courses)
- All AEs
- Drug-related AEs
- AEs leading to dose reduction
- AEs leading to treatment discontinuation
- Drug-related AEs leading to dose reduction
- Drug-related AEs leading to treatment discontinuation
- AEs leading to death
- Serious AEs
- Drug related serious AEs
- Other significant AEs, defined as AEs leading to dose reduction or permanent discontinuation of study medication
- Non-serious AEs with higher than 5% occurrence rate for disclosure on ClinicalTrials.gov

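### SAP Table 6.1:1 closes the Off-treatment period at the follow-up visit, contradicting the open-ended rule in SAP 7.8.1 and the post-study review in protocol 7.3.3

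*SAP*

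**What the plan says.** SAP 6.1 sets up Table 6.1:1 "for reporting of treatment emergent AEs and safety laboratory data". Its assignment rule begins "An adverse event will be assigned to the analysing period where start date" and places an event in a period when start ≤ onset < stop. Off-treatment starts, inclusively, at "Date of last intake of study drug + 29 day". It stops, exclusively, at "Date of last follow up visit + 1 day or date of death + 1 day whichever occurred first".

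SAP 7.8.1 gives a different rule for the same period: "all adverse events occurring after last study drug intake + 28 days will be assigned to 'Off-treatment' (for listings only"). It states no stop date, but it then sends the reader back to Section 6.1 for the period definitions.

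Protocol 7.3.3 treats events up to 28 days after the last dose as on treatment and continues: "In general later events will be attributed to the post-study period and will be presented separately". It adds that these post-study events are to be looked at to decide whether an additional table should combine them with on-treatment events.

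Two further protocol provisions fix the timing and content of follow-up:

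- Flow chart, footnote 3: "FU= safety follow-up 28 to 30days after last afatinib administration". Protocol 6.1 calls this the last safety visit and the patient's end-of-trial visit. Footnote 4 of the flow chart says the later observation period needs no formal visit.
- Protocol 5.2.2.2: "SAEs and AESIs occurring after the FU visit (28-30 days after last administration of study medication) will be reported in case they are considered relevant". Relevance is the investigator's judgement. Table 5.2.2.2:1 has the same provision for SAEs.

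**The concern.** The protocol deliberately keeps a channel open for late events after the follow-up visit, limited to those the investigator considers relevant. The SAP table that allocates events to periods closes the last period at, or almost at, that same visit. A programmer who derives the period variable from Table 6.1:1 would find no period for these events. One who works from SAP 7.8.1 would put them all in Off-treatment.

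What is at stake is the completeness of the Off-treatment listing, and of the set of events brought to the review in protocol 7.3.3. The trial is described as the first in children with this drug (protocol 2.3) and is small, with up to 55 patients, so each late relevant SAE carries weight. SAP 7.8.2 has the same dependency: it promises listings of post-treatment laboratory data and also refers to Section 6.1 for the periods.

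**Working it through.** Let L be the date of last intake and FU the date of the follow-up visit.

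**Inputs**

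- Off-treatment start, included: L+29 (SAP Table 6.1:1).
- Off-treatment stop, excluded: FU+1, or death+1 if earlier (SAP Table 6.1:1).
- Assignment rule: start ≤ onset < stop (SAP 6.1).
- On-schedule FU: L+28 to L+30 (protocol flow chart, footnote 3).
- Rule in the AE section: every onset after L+28 is Off-treatment, with no stop (SAP 7.8.1).

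**Check of the reading against a stated figure.** The residual effect period in the same table runs from L+1 (included) to L+29 (excluded). Its length is 29 − 1 = 28 days. This reproduces the 28 days stated in SAP 6.1, so the inclusive/exclusive reading is the intended one.

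**Length of Off-treatment under the table.** Length = (FU+1) − (L+29), not below zero.

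| FU visit | Calculation | Length |
|---|---|---|
| L+28 | 29 − 29 | 0 days |
| L+29 | 30 − 29 | 1 day |
| L+30 | 31 − 29 | 2 days |

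A visit outside the window changes this. As an assumed example, FU at L+37 gives 38 − 29 = 9 days. Death on or before L+28 gives 0 days. Death after the FU visit does not lengthen the period, because the earlier of the two dates applies.

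**Where a late event lands under each rule**

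| Onset | Table 6.1:1, FU at L+28 | Table 6.1:1, FU at L+30 | SAP 7.8.1 |
|---|---|---|---|
| L+28 | On-treatment | On-treatment | On-treatment |
| L+29 | none | Off-treatment | Off-treatment |
| L+30 | none | Off-treatment | Off-treatment |
| L+31 | none | none | Off-treatment |
| L+45 | none | none | Off-treatment |
| L+84 | none | none | Off-treatment |
| L+120 | none | none | Off-treatment |

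The two rules agree on where Off-treatment begins: after L+28 is the same as from L+29. They differ only on where it ends. The on-treatment boundary (L+29, excluded) is the same in both, so nothing summarised on treatment moves.

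**The case against.** The strongest reply is that SAP 7.8.1 already gives these events a home. It is the SAP's specific instruction for adverse events, it covers every event after L+28, and it has no end date. Protocol 7.3.3 defines its post-study events by the 28-day limit and not by Table 6.1:1. The SAP says it is based on protocol Section 7, and SAP Section 4 does not withdraw that review. Off-treatment events are only listed, and all analyses are descriptive. Closing a period at the end of trial participation is also coherent in itself.

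Most of this stands, and it rules out three stronger readings that a reader might infer:

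- **That late events belong to no analysis period.** This is true of Table 6.1:1 alone. SAP 7.8.1 and protocol 7.3.3 both place them.
- **That late events will be dropped, or that the 7.3.3 review will run on an almost empty set.** This would follow only if the table were programmed in preference to 7.8.1 and also used to select events for the review. The documents do not say so.
- **That late fatal events are generally lost.** A fatal event with onset on treatment is still captured, and one with onset after L+28 is Off-treatment under 7.8.1. Deaths from progression of the malignancy are exempt from (S)AE reporting (protocol 5.2.2.1).

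It can also be said that the SAP does not define the last follow-up visit, so the term might cover observation-period contacts. That is possible, but protocol 6.1 attaches almost the same words to the visit at day 28 to 30, and the later contacts are not formal visits.

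The reply does not remove the contradiction. SAP 7.8.1 refers back to Section 6.1 for the definitions, and there the reader meets the closed stop date and a literal assignment rule. The July 2020 history entry says the period definitions were clarified, which makes it reasonable to treat the table as authoritative.

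**Conclusion.** The table is wrong as written, with minor impact. SAP Table 6.1:1 and SAP 7.8.1 give incompatible ends to the same period, and the table also does not fit the open-ended post-study period in protocol 7.3.3. With an on-schedule follow-up visit the table's Off-treatment period lasts 0 to 2 days, and an SAE or AESI with onset after that visit matches no row.

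No on-treatment adverse event, DLT or laboratory summary is affected. The exposure is confined to late relevant events being missing from the Off-treatment listing and from the input to the 7.3.3 review, and it is conditional on programming following the table. The documents do not show how many such events there would be.

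The conclusion assumes that the last follow-up visit means the protocol's single FU visit. The 0 to 2 days further assumes that the visit takes place within its window; a later visit lengthens the period but still leaves events after it outside the table.

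**What to change.** In Table 6.1:1, remove the follow-up-visit limit and make the Off-treatment stop date open-ended, as in SAP 7.8.1. If a calendar date is needed for programming, use death + 1 day or, for patients alive, last contact (including observation-period contacts) or data cut-off, + 1 day. If the sponsor did mean the present wording to reach observation-period contacts, the SAP should define the last follow-up visit that way.

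The cost is one table cell and one derivation line. No new data are needed, and no on-treatment output has to be re-run.

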6.2 IMPORTANT PROTOCOL DEVIATIONS

A protocol deviation is important if it affects the rights or safety of the study patients, or if it can potentially influence the primary outcome measurements in a non-negligible way. Patients with important protocol deviations (IPDs) that could potentially impact the evaluation of the primary endpoint(s) will be excluded.

The different categories of IPDs are defined in Table 6.2: 1. IPDs will be reviewed at Medical Quality Review Meetings (MQRMs) conducted periodically during the trial. A list of protocol deviations will be discussed at the report planning meetings (RPMs). If the data show other IPDs, this table will be supplemented accordingly at MQRMs or RPMs or through team review of the protocol deviation log. The decision whether a patient will be excluded from the analysis will be made at the final RPM prior to DBL.

Table 6.2: 1 Important protocol deviations

Category/ Code	Description	Comment/Example	Excluded from	Manual/ Automatic
A	Inclusion/Exclusion Criteria			
A1				
A1.1	Laboratories measurements	Exclusion criteria 13,14,15	None	Automatic
A1.2	Forbidden concomitant diagnoses	Exclusion criteria 4,5,7,9,10,11,12	None	Automatic
A1.3	Female patients who are pregnant or doing breast feeding at baseline	Exclusion criteria 6	None	Automatic
A1.4	Prohibited concomitant medications, radiotherapy and surgery	Exclusion criteria 1,2,3, 8	None	Automatic
A2				Automatic
A2.1	Patient does not have trial diagnosis	Inclusion criteria 1	None	Automatic
A2.2	Patient did not recover (to CTCAE grade 1 or baseline) from any acute toxicity resulting from prior anti-cancer treatment (except alopecia)	Inclusion criteria 4	None	Automatic
A2.3	Patient did not have Lansky/Karnofsky (depending on age) scores $\geq 50\%$ assessed within 2 weeks prior to enrolment.	Inclusion criteria 8	None	Automatic
A2.4	Patient has LVEF $< 50\%$	Inclusion criteria 12	None	Automatic
A2.5	Required ErbB pathway deregulation absent	MTD Expansion Cohort: Inclusion criteria 1 or 13	None	Automatic
A2.6	Patient age at study start not between ≥ 2 to < 18 years Patient age at study start not between ≥ 1 to < 18 years	Dose finding cohort: Inclusion criteria 3 MTD expansion cohort: Inclusion criteria 3	None	Automatic
A2.7	No tumour tissue available (exception of DIPG)	MTD Expansion Cohort: Inclusion criteria 7	None	Automatic
A2.8	Patient do not have at least one measurable lesion according to the institutional response criteria for the given tumour type.	Inclusion criteria 14	None	Automatic

Table 6.2: 1 Important protocol deviations (cont.)

Category/ Code	Description	Comment/Example	Excluded from	Manual/ Automatic
B	Informed Consent			Automatic
B1	Informed consent not given	Inclusion criterion 6	All	Automatic
B2	Informed consent after administration of trial medication	Inclusion criterion 6	None	Automatic
B3	Informed consent not in accordance with regulations		None	Manual
C	Trial Medication			
C1	Dose change of afatinib not according to protocol		None	Manual
C2	Non-compliance	Afatinib not taken according to protocol	None	Manual
C3	Dose reduction/paused/discontinuation not according to protocol following an AE/DLT	Refer to Table 4.1.2.3:1 and Table 4.2.2.1:1 in the CTP	None	Manual
D	Concomitant Treatment			
D1	Any other chemotherapy, immunotherapy or radiotherapy during the trial except for palliative radiation	Refer to Section 4.2 of the CTP	None	Manual
D2	During palliative radiation, treatment was not paused until the patient recovered from any radiation associated toxicity	Refer to Section 4.2 of the CTP	None	Manual
D3	Continuous interruption of >28 days due to palliative radiotherapy	Refer to Section 4.2 of the CTP	None	Manual
E	Critical study procedure			
E1	Critical study procedure not followed		None	Manual
F	Privacy / data protection			
F1	Privacy and/or data protection violated		None	Manual

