7.3 PLANNED ANALYSES

All patients who receive at least one dose of afatinib will be included in the analysis for safety and efficacy and they are defined as treated set.

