7.3.1 Primary analyses

Dose finding part:

In order to determine the MTD, the number of patients with DLT deemed to be related to administration of afatinib will be assessed based upon the patients in dose finding part of the trial. (See [Table 4.1.4.1:2](#)). The advanced disease of the patients in this trial makes it possible that significant adverse events, including events that would qualify as DLT, will occur, but will not be caused by afatinib. The MTD will be determined as the highest dose at which no more than 1/6 patients experienced DLT considered related to afatinib. (See [Table 4.1.4.1:1](#))

Proprietary confidential information.

© 2017 Boehringer Ingelheim International GmbH or one or more of its affiliated companies. All rights reserved.

This document may not - in full or in part - be passed on, reproduced, published or otherwise used without prior written permission.

Pharmacokinetics is a primary endpoint for the dose finding part. For details see [Section 7.3.5](#)

MTD expansion cohorts/Phase II part:

OR will be assessed when the last patient enrolled in the MTD expansion cohorts/Phase II part will be evaluable for efficacy.

Each patient will be assigned to one of the following categories based on investigator's assessment according to the institutional response evaluation criteria for the given tumour type, irrespective of protocol violation or missing data:

- CR (complete response)
- PR (partial response)
- SD (stable disease)
- PD (progressive disease)
- Not evaluable (not assessable, insufficient data)

Objective response is defined as CR and PR.

If the International Criteria for Neuroblastoma Response Criteria (INRC) ([R14-2418](#)) is used, each patient will be assigned to one of the following categories:

- CR (complete response)
- VGPR (very good partial response)
- PR (partial response)
- MxR (mixed response)
- NoR (no response)
- PD (progressive disease)

The objective response is then defined as CR, VGPR, PR or MxR.

OR will be tabulated and provided with the proportion and the exact 95% confidence interval based on all treated patients in the MTD expansion cohorts/Phase II part.

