7.4 PRIMARY ENDPOINT(S)

7.4.1 Dose Finding Part:

One of the primary objectives is to assess the MTD based on the number of patients presenting DLTs during the MTD evaluation period. Therefore, an overall summary of DLTs (see CTP Section 4, Table 4.1.4.1.2 for the definition of DLTs) which occurred during the MTD evaluation period will be provided for each dose cohort from the dose finding cohort treated set. Patients who were replaced within the MTD evaluation period will be excluded from the determination of the MTD but will be considered for all other safety evaluations.

A summary of the number of patients with DLTs overall in any course will be also given by initial treatment and displayed in a similar format to the summary of DLTs occurring in the MTD evaluation period.

The determination of the MTD is based on a Rolling 6 design as illustrated in Section 4, Table 4.1.4.1:1 of the CTP. The MTD is defined as the highest dose at which no more than 1/6 patients experienced DLT considered related to afatinib during the MTD evaluation period. Refer to CTP 7.3.1 for further details on MTD evaluation.

Analysis of the standard PK endpoints is performed according to (2) and (8) as outlined in Section 7.3.5 of the CTP.

7.4.2 MTD expansion cohort part:

Objective response (OR) is defined as a best overall response of complete response (CR) or partial response (PR) based on investigator's assessment according to the institutional

response evaluation criteria for the given tumour type. If the International Criteria for Neuroblastoma Response Criteria (INRC) is used, OR is defined as complete response (CR), very good partial response (VGPR), partial response (PR) and mixed response (MxR). For further details on OR, please refer to CTP Section 7.3.1. The objective response rate will be calculated and reported as proportion of responders with 95% Clopper-Pearson CIs based on all treated patients. Objective response will be summarized regardless of confirmation.

Additional summary or listing may be provided for confirmed response. If only few patients (fewer than 5) achieved objective response, a detailed listing will be reported.

For objective responses, evaluated by institutional response evaluation criteria other than INRC, below confirmation rule for best overall response will be considered.

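### SAP 6.2 orders exclusion of patients whose deviations could affect the primary endpoint, which for objective response contradicts the SAP's own deviation table, SAP 7.4.2 and the protocol's all-treated analysis

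*SAP*

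**What the plan says.** SAP 6.2 gives a general exclusion rule for important protocol deviations (IPDs): "Patients with important protocol deviations (IPDs) that could potentially impact the evaluation of the primary endpoint(s) will be excluded". On timing it says: "The decision whether a patient will be excluded from the analysis will be made at the final RPM prior to DBL". The list of IPDs is not closed: "If the data show other IPDs, this table will be supplemented accordingly at MQRMs or RPMs".

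The other provisions that bear on OR point the other way:

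- **SAP Table 6.2:1.** Every coded row has None in the column for exclusion except B1 ("Informed consent not given"), which has All.
- **SAP 7.4.2.** The response rate is the "proportion of responders with 95% Clopper-Pearson CIs based on all treated patients".
- **Protocol 7.3.** "All patients who receive at least one dose of afatinib will be included in the analysis for safety and efficacy".
- **Protocol 7.3.1.** Each patient gets a response category "irrespective of protocol violation or missing data", and the rate is given with an "exact 95% confidence interval based on all treated patients in the MTD expansion cohorts/Phase II part".

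SAP Section 4, which records changes to the planned analysis, does not mention an exclusion rule.

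**The concern.** SAP 5.1 and protocol Section 5 make OR the primary endpoint of the expansion part, so the SAP 6.2 sentence applies to it as written. An analyst who follows that sentence removes patients from the primary response rate. One who follows Table 6.2:1, SAP 7.4.2 or the protocol keeps them. The SAP does not say which rule prevails.

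Timing makes this more than an editorial matter. Treatment is open-label and the investigator assesses response, so responses can be known by the final RPM. A rule that leaves exclusions from the primary analysis to that meeting, with a deviation list that can grow from the data, allows removal after the outcome is known. Nothing in the documents says exclusions would be chosen by response, but the sentence does not prevent it. Protocol 3.2 ties further development to whether experts and regulators find the response rate meaningful, so its denominator should not be open to two readings.

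**Working it through.** **1. Does the sentence reach OR?** It refers to the primary endpoint(s) without restriction. SAP 5.1 lists DLT and PK for dose finding and OR for the expansion part. Protocol 4.1.3 records dose finding as completed, and the SAP was last revised in July 2020 (SAP Section 10). OR was therefore the primary endpoint still to be analysed.

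**2. Rules side by side for deviations that could plainly affect OR.**

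| Deviation (SAP Table 6.2:1) | SAP 6.2 text | Table 6.2:1 | SAP 7.4.2; protocol 7.3, 7.3.1 |
|---|---|---|---|
| A2.8 no measurable lesion | excluded | None | included if treated |
| C2 non-compliance | excluded | None | included if treated |
| D1 other anti-cancer therapy | excluded | None | included if treated |
| B1 no consent | excluded | All | no exception stated |

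In the first three rows the text and the other rules cannot both be followed.

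**3. Where the sentence can legitimately apply.** DLT evaluability (SAP 5.1), replaced patients (SAP 7.4.1) and the PK analysis set (SAP 6.3) each have their own exclusion rules. SAP 6.2 is not limited to these.

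**4. A linked inconsistency in SAP 6.3.** The MTD expansion cohort treated set requires biomarker positivity or a proven ErbB alteration as well as one dose. Table 6.2:1 row A2.5 (required deregulation absent) says None, and protocol 7.3 requires only one dose. Biomarker status is settled before entry (protocol 3.3.2 and 4.1.2), so this affects only a patient dosed despite failing the criterion. It is not a route to selection after outcome.

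**5. Size.** The plan gives no figure to reproduce. Inputs from the protocol synopsis are the expansion maximum of 38 patients evaluable for OR and the cohort minimum of 5. Responder counts and numbers excluded are assumed. For x responders in n patients, the exact 95% limits are the 0.025 quantile of Beta(x, n − x + 1) and the 0.975 quantile of Beta(x + 1, n − x); the lower limit is 0 when x = 0.

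| Scenario | x/n | Rate | Exact 95% CI |
|---|---|---|---|
| All treated | 4/38 | 10.5% | 2.9% to 24.8% |
| Four non-responders dropped | 4/34 | 11.8% | 3.3% to 27.5% |
| One responder dropped | 3/37 | 8.1% | 1.7% to 21.9% |
| Cohort of five, all treated | 1/5 | 20.0% | 0.5% to 71.6% |
| One non-responder dropped | 1/4 | 25.0% | 0.6% to 80.6% |
| The responder dropped | 0/4 | 0% | 0% to 60.2% |

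Pooled shifts: 11.76 − 10.53 = 1.2 points up, and 10.53 − 8.11 = 2.4 points down. The 4/38 interval is 24.8 − 2.9 = 21.9 points wide. In the cohort of five, one exclusion moves the rate up 5 points or down 20.

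**The case against.** The strongest reply is that the specific rules already agree. The table gives each deviation a disposition, SAP 7.4.2 and the protocol name the denominator, and a reader who puts specific rules above general ones reaches a single answer. No per-protocol set is visible: PPS appears in the SAP's abbreviation list, but SAP 6.3 does not define one. The sentence may be leftover template text, and it has a natural use for DLT and PK. A pre-lock meeting is needed in any case to settle PK-set membership and B1.

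Much of this is fair as a guess at intent, but the SAP states no order of precedence. The table can be supplemented, and nothing fixes a new row at None. A missing per-protocol set makes the sentence less clear, since it then names no population from which patients are removed.

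Some limits on weight do stand. The magnitudes rest on assumed counts. The figure of 38 is patients evaluable for OR, and withdrawn patients may be replaced (protocol 3.3.4.1), so the treated number could be higher. SAP 7.4.2 specifies no response rate by cohort, so the five-patient figures are illustrative only. With fewer than five responders, as in every scenario above, SAP 7.4.2 calls for a detailed listing, which would help make an exclusion visible. Protocol 7.3 has no consent exception, so keeping B1 follows the SAP's table rather than the protocol.

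**Conclusion.** The concern holds. For objective response, SAP 6.2 as written contradicts Table 6.2:1, SAP 7.4.2 and protocol 7.3 and 7.3.1, and SAP Section 4 declares no such change. This rests on the text alone and needs no numerical assumption.

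The practical consequence is moderate. All analyses are descriptive (protocol 7.2), so no type I error is at stake, and under the assumed counts the pooled rate moves by far less than the width of its interval. A single exclusion in a cohort of about five would be more visible. The point should be fixed because it concerns the primary denominator in an open-label trial and the correction is simple. The SAP 6.3 condition is a lesser inconsistency to correct at the same time.

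**What to change.** In SAP 6.2, remove the exclusion sentence and the final-RPM exclusion decision as they apply to OR, PFS and DoR; the two secondary endpoints are included because protocol 7.3 covers all efficacy analyses. State that for these analyses only B1 removes a patient, and that IPDs added later are listed without changing the efficacy population. Leave the DLT-evaluability rule (SAP 5.1), the replacement rule (SAP 7.4.1) and the PK-set exclusions (SAP 6.3) unchanged, and refer to them by section.

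In SAP 6.3, define the MTD expansion cohort treated set as all patients entered in the expansion part who took at least one dose. A response rate restricted to patients meeting inclusion criterion 1 or 13 can be added as a sensitivity analysis if wanted.

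The cost is SAP wording in two sections, with no new data or patients. The downside is that an ineligible treated patient stays in the denominator, as the protocol already requires.
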